10.5 REPORTING OF SUSARS TO LOCAL HEALTH AUTHORITY

The study sponsor is responsible for submission of reportable SUSARs to the local Health Authority according to regulatory requirements. The timeline for reporting any suspected adverse reaction that is both serious and unexpected is **15 calendar days** after the investigator determines that the suspected adverse reaction qualifies for reporting.

The timeline for reporting any suspected adverse reaction that is both serious and unexpected is **7 calendar days** for events that are fatal or life threatening.

11. STATISTICAL METHODS

11.1 SAMPLE SIZE ESTIMATION & JUSTIFICATION

The primary comparison for study is the level of plasma HIV RNA on day 11 during disulfiram/vorinostat treatment compared to baseline. Based on two previous studies of LRAs, where treatment with disulfiram 2000 mg or romidepsin led to increases in plasma HIV RNA^{4,6}, we assume a pre-study therapy mean of 1 copy/mL and a standard deviation of 11 copies/mL for the increase in plasma HIV RNA. Based on these numbers, the study will require 14 participants to detect an increase in plasma HIV RNA of 10 copies/mL with 80% power at a 0.05 significance level. Targeted enrolment is 15 participants to accommodate for loss to follow-up.

No interim analysis is planned.

11.2 ANALYSES OF PRIMARY AND SECONDARY ENDPOINTS

The primary comparisons will be made using paired t-test or signed-rank test as appropriate. By applying the same statistical methods, we will also analyse whether changes in CA-US HIV RNA and plasma HIV RNA differ following administration of high dose disulfiram and vorinostat. We will use repeated measurement analysis of variance statistics and/or generalized estimating equation statistics to analyse overall changes in primary and secondary endpoints during study intervention by including all data points during study therapy. P-values <0.05 will be considered significant.

The tolerability population will include all participants who have received at least one dose of vorinostat or disulfiram. Adverse events (AEs) and serious adverse events (SAEs) will be summarized according to severity assessment showing the number and percentage of participants experiencing at least one event, the number of events, and the causality assessment. No formal statistical comparisons will be made – AE rates are presented for descriptive purposes.

11.3 GENE EXPRESSION DATA AND ADDITIONAL ANALYSES TO INVESTIGATE NEUROTOXICITY (SECTIONS 9.8 – 9.12)

RNA sequencing data will undergo standard bioinformatic analyses, which is performed by Australian Genome Research Facility (AGRF), Melbourne. This will include quality and adapter trimming, alignment, quantification and normalisation. RNA expression data will be mapped to a reference genome and gene expression levels will be compared across different time points to identify differentially expressed genes. Differential expression of gene pathways will be analysed using Kyoto Encyclopedia of Genes and Genomes (KEGG) and Reactome platforms.

Other additional analyses related to observed neurotoxicity include plasma levels of cytokines, biomarkers of neuronal injury, levels of histone acetylation, pTEFB and NFkB activation and effects of disulfiram with or without vorinostat on primary astrocytes, astrocyte cell lines and PBMCs. These data will be summarised using descriptive statistics. Where feasible different time points or conditions will be compared using paired t-test or signed-rank test.

12. STORAGE OF BLOOD SAMPLES

Blood samples will be collected for PBMC and plasma storage at each visit as indicated in section 8 of this protocol. Samples will be stored at the Doherty Institute, University of Melbourne ([name] Laboratory) and will only be accessible to research staff following approval by the Protocol Steering Committee, which will include [name], [name], [name] and a community representative. Stored samples may be used for future analyses conditioned on adherence to local regulations and ethical guidelines and approval of human research ethics committee.

13. ETHICAL CONSIDERATIONS

13.1 STUDY APPROVAL

Sponsor must obtain prospective approval before study initiation of the study protocol, informed consent documents and other relevant documents from the HREC and the Therapeutic Goods Administration (TGA) through the Clinical Trial Notification (CTN) scheme.

13.2 ETHICAL CONDUCT OF THE STUDY

The Sponsor and principal investigator is responsible for planning and conducting the study in accordance with The Helsinki Declaration (1996 version), guidelines for Good Clinical Practice (GCP; International Conference on Harmonization 1996), and Australian ethical guidelines and law.

13.3 HREC REVIEW AND INFORMED CONSENT

This protocol, the informed consent document and any subsequent modifications will be reviewed and approved by the HREC responsible for oversight of the study. A signed consent form will be obtained from each study participant prior to any study procedures. The consent form will describe the purpose of the study, the procedures to be followed, and the potential risks and benefits of participation. A copy of the consent form will be given to the study participant, parent, or legal guardian. During the informed consent process, research staff will ensure that potential participants understand the purpose of the study, the study intervention, study procedures, any risks associated with participation and that participation is voluntary. Any questions posed during the informed consent process or subsequently during the study will be carefully addressed. Potential participants will be given as much time as they need to read and understand the consent form.

13.4 HARMS, RISKS AND INCONVENIENCES

The potential harms, risks and/or inconveniences associated with participation in this study will be that of exposure to the study drugs disulfiram and vorinostat, the risk of phlebotomy, the risk of pregnancy in women of childbearing potential and the inconveniences associated with attending study visits. To monitor the safety and ensure the well-being of study participants, monitoring and handling of adverse events will be done at study visits as detailed in section 8 and 10 of this protocol. In the event of adverse effects, participants will have

medical care available through the Alfred Hospital. Any medical testing and evaluation undertaken by study investigators to follow up abnormal findings will also be at no cost to participants.

13.4.1 Disulfiram

Undesirable effects of disulfiram are reported in individuals that have not abstained from alcohol, which results in a disulfiram-ethanol toxic reaction, as specified in the product information and includes an intense cutaneous flushing from the head downwards, involving the face, sclera, upper limbs, and chest. The cutaneous flushing is caused by vasodilation and is accompanied by a sensation of heat and sweating, palpitations, with tachycardia, dyspnoea, hyperventilation and the patient develops a pounding headache. There is a feeling of constriction and irritation of the throat and trachea, resulting in spasms of coughing. Chest pains may occur simulating coronary spasm. Restlessness or a sense of uneasiness and fear of dying may develop. These symptoms are accompanied by a steep rise in blood pressure, followed by hypotension if vasodilation is significant. Flushing is then replaced by pallor, weakness, vertigo, and nausea develops that turns into violent vomiting with abdominal cramps. Other symptoms reported include thirst, dizziness, blurred vision, numbness of hands and feet, and insomnia. Severe reactions may affect the heart, and there may be convulsions, loss of consciousness, and death from cardio-respiratory failure.

The intensity of the reaction varies with the individual and the duration of the reaction continues as long as there is ethanol in the blood. Confusion, drowsiness and sleep usually follow. Frequently, there are transient ECG changes, such as flattening of T waves, depression of S-T segment, and Q-T prolongation in a pattern suggestive of right ventricular strain.

13.4.2 Vorinostat

The most common drug-related adverse reactions, which have been reported in cancer patients can be classified into 4 symptom complexes.

1. Gastrointestinal symptoms. Anorexia, nausea, vomiting, diarrhoea, weight loss and constipation have been reported. Antiemetic and antidiarrheal medications have been used with good effect. Fluid and electrolyte replacement may be required. Patients should be encouraged to drink at least 2L of fluid each day, and aggressive management of nausea and diarrhoea is strongly encouraged, to avoid renal impairment secondary to dehydration.
2. Constitutional symptoms. Fatigue has been reported commonly with use of vorinostat and occurred more commonly at doses of vorinostat greater than 400mg per day. Chills and fever have also been reported.
3. Hematologic abnormalities. Dose-related anaemia and thrombocytopenia can occur with vorinostat and are more common at doses of more than 400mg per day. Neutropenia is uncommon, but has been reported. Monitoring of blood cell counts should be performed every 2 weeks during the first 2 months of therapy and monthly thereafter. If platelet counts and/or haemoglobin are reduced during treatment with vorinostat, the dose should be modified or therapy discontinued.
4. Taste disorders. Dysgeusia and dry mouth have been reported with use of vorinostat.

The most common serious adverse events, regardless of causality, in the 86 CTCL patients in two clinical studies were pulmonary embolism reported in 4.7% (4/86) of patients, squamous

cell carcinoma reported in 3.5% (3/86) of patients and anaemia reported in 2.3% (2/86) of patients. Patients on vorinostat should therefore be monitored for pertinent signs or symptoms of deep vein thrombosis or pulmonary embolism.

Of the CTCL patients who received the 400-mg once daily dose, 9.3% (8/86) of patients discontinued vorinostat due to adverse events and 10.5% (9/86) of patients required a dose modification due to adverse events. The median time to the first adverse event resulting in dose reduction was 42 days (range 17 to 263 days).

Laboratory abnormalities were reported in the 86 patients who received the 400-mg dose and one patient who received a 350-mg dose.

Increased serum glucose was detected by laboratory safety tests in 69% (60/87) of CTCL patients, but was severe (Grade 3) in only 5 of these. Hyperglycaemia was reported as a drug-related adverse experience in 4.7% (4/86) of CTCL patients who received the 400-mg once daily dose. Serum glucose should be monitored, especially in diabetic or potentially diabetic patients. Adjustment of diet and/or therapy for increased glucose may be necessary. Blood glucose monitoring of diabetic patients is recommended.

Transient increases in serum creatinine were detected in 47.1% (41/87) of CTCL patients; in most cases these increases were non-severe, however, Grade III (severe) cases have been observed. Based on reports of dehydration as a serious drug-related adverse experience in clinical trials, patients were instructed to drink at least 2 L/day of fluids for adequate hydration. After these precautions were implemented, the incidence of dehydration decreased.

Proteinuria was detected as a laboratory abnormality (51.4%) in 38 of 74 patients tested. The clinical significance of this finding is unknown.

A phase 1 study has been performed of 25 patients given a single suprathreshold dose of vorinostat 800mg. Of the 24 patients included in analysis, no patient had a significant change in QTc over 24 hours of monitoring. In other studies three of 86 CTCL patients exposed to 400mg once daily had Grade 1-2 QTc prolongation. In a retrospective analysis of three Phase I trials and two Phase II trials, 4 of 116 evaluable patients had grade 2 QTc prolongation, and 1/116 had grade 3 QTc prolongation. Of 49 non-CTCL patients from 3 clinical trials 1 had grade 2 prolongation and 2 had grade 3 QTc prolongation. Baseline and periodic ECGs should be performed during treatment. Vorinostat should be administered with particular caution in patients with congenital long QT syndrome, and patients taking anti-arrhythmic medicines or other medicinal products that lead to QT prolongation. Hypokalemia or hypomagnesemia should be corrected prior to administration of vorinostat, and consideration should be given to monitoring potassium and magnesium in symptomatic patients (e.g., patients with nausea, vomiting, diarrhoea, fluid imbalance or cardiac symptoms).

13.4.3 Reproductive risks

Safe use of either disulfiram or vorinostat in human pregnancy or during lactation has not been established.

Available reproductive toxicity studies in animals do not necessitate that females of childbearing potential are excluded from clinical trials of disulfiram or vorinostat, but use of effective contraception for both males and females are required for participation in this study. In addition, for female participants, a negative pregnancy tests is required during screening.

13.4.4 Phlebotomy

Phlebotomy may cause some discomfort, bleeding or bruising where the needle enters the skin, and rarely, fainting or infection may occur.

13.5 RISK/BENEFIT ANALYSIS

Even though the implementation of combination ART to treat HIV infection has had a tremendous impact on the epidemic by restoring the health of well-treated individuals, HIV infection remains a major public health challenge world-wide. Moreover, as ART discontinuation invariably results in viral rebound to pre-treatment levels, the development of a cure for HIV continues to be a fundamental goal in infectious disease research. Although the initial studies of LRAs showed no decline in latently infected cells, it is likely that an effective intervention to reverse latency will be needed in combination with interventions that eliminate latently infected cells. Identification of safe interventions that can increase potency of latency reversal remains a high scientific priority.

The design of the study with a relatively short administration of the well-studied and safe drug disulfiram, together with a short period of administration of vorinostat to background ART is aimed at increasing the potency of latency reversal. As such, it is unlikely that participation is associated with any sustained significant clinical benefit for the participants. Hence, any benefits accrued by completing this study will primarily be for society rather than the individual study participant.

The harms, risks and inconveniences associated with study participation are outlined above and include known and unknown adverse effects of both disulfiram and vorinostat, reproductive risks and phlebotomy. These risks have been minimized by choosing a relatively short period for the study intervention, by excluding candidates with any condition that would increase the risk of adverse effects and by the proper conduct and monitoring of the study. Given these considerations, we believe that this study is ethically and scientifically justified.

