6.3 EXCLUSION CRITERIA

- Current alcohol use disorder or hazardous alcohol use (>7 drinks per week for women or > 14 drinks per week for men) as determined by clinical evaluation
- Current or recent (in the last 4 days) use of metronidazole or any drug formulation that contains alcohol or that might contain alcohol, including the gelatin capsule and liquid formulations of ritonavir, ritonavir/lopinavir, amprenavir and fosamprenavir,

and alcohol-containing preparations such as cough syrups, tonics etc.

- Current use of tipranavir or Maraviroc
- Current use of zidovudine, stavudine or didanosine (as disulfiram potentially has potent irreversible inhibitory effects on mitochondrial metabolism and hence could exacerbate the toxicity of these drugs)
- Concurrent use of rivaroxaban (a CYP3A metabolized medication) as the cytochrome P450 inhibitory effects of disulfiram on rivaroxaban are unknown
- Current use of warfarin
- Individuals who intend to modify antiretroviral therapy during the study period for any reason
- Significant myocardial disease (current myocarditis or reduced left ventricular ejection fraction below the lower limit of normal) or diagnosed coronary artery disease
- Significant renal disease (eGFR <50mL/min)
- History of psychosis, seizure disorder, abnormal electroencephalogram or brain damage with significant persisting neurological deficit
- Prior malignancy active within the previous 3 years except for local curable cancers that have been apparently cured, such as basal or squamous cell skin cancer, superficial bladder cancer or carcinoma in situ of the prostate, cervix or breast.
- Known hypersensitivity to disulfiram or vorinostat or contraindications to treatment with these agents
- Participation in another LRA study or receipt of vorinostat or disulfiram in the previous 12 months before starting the investigational treatment (visit #2)
- Any significant acute medical illness requiring hospitalization within preceding 8 weeks
- Hepatitis B or C co-infection as determined by detection of HBsAg or HCV RNA (Individuals with prior hepatitis infection that is now cleared are eligible for enrolment)
- Receipt of immunomodulating agents (excluding immunization) or systemic chemotherapeutic agents within 28 days prior to study entry
- Current or recent gastrointestinal disease or surgery that may impact the absorption of the investigational drug

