- Active substance use that in the opinion of the investigator will prevent adequate compliance with study procedures
- Women who are currently pregnant or breastfeeding
- Women of Child Bearing Potential (WOCBP) who are unwilling or unable to use an acceptable method of contraception to avoid pregnancy (as specified in the inclusion criteria, section 6.2)
- Unable or unwilling to adhere to protocol procedures
- The following laboratory values within 6 weeks before starting the investigational drug (lab tests may be repeated to obtain acceptable values before failure at screening is concluded)
 - Hepatic transaminases (AST or ALT) ≥ 3 x upper limit of normal (ULN)
 - Serum total bilirubin ≥ 1.5 x ULN
 - eGFR <50 mL/min
 - Haemoglobin <10.0 g/dL
 - Platelet count $\leq 100 \times 10^9/L$

- Absolute neutrophil count $\leq 1.5 \times 10^9/L$
- Serum potassium, magnesium, phosphorus outside normal limits
- Total calcium (corrected for serum albumin) or ionized calcium \leq lower normal limits

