6.5 WITHDRAWAL FROM THE INVESTIGATIONAL DRUG(S)

Withdrawal from the investigational drug(s) is defined as any participant who discontinues study treatment but agrees to a modified follow-up until completion of the study. Any participant who withdraws from the investigational drug after having received at least one dose will be asked to return for a follow-up visit 1 week after withdrawal from the study treatment (safety monitoring) and the final follow-up visit as described in this protocol.

Reasons why a study participants may be withdrawn from the investigational drug(s) include, but are not limited to:

- Participant request (withdrawal of consent)
- Adverse events or reactions
- Pregnancy
- Any condition, interaction, or contraindication where continued participation in the study will result in an unacceptable risk for the participant, as assessed by the investigators.

Information related to withdrawal from the investigational drug/placebo is documented in the eCRF (End of Study) including the reason for withdrawal, date of withdrawal, and whether the participant or investigator made this decision. If withdrawal from the investigational drug/placebo is due to an adverse event, this will be followed up as detailed under adverse event report in this protocol.

Participants withdrawn from the investigational drug(s) will resume routine treatment and monitoring at either the Department of Infectious Diseases, Alfred Hospital, Melbourne.

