7.7 CONCOMITANT THERAPY ALLOWED DURING THE STUDY

Any treatment that is considered necessary for the participant's welfare (including supportive therapy) and which, in the opinion of the investigator, will not interfere with the study therapy, may be given at the discretion of the investigator. Specifically, vaccines that are part of a recommended immunization schedule or used in the event of a disease outbreak are allowed during study therapy.

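### Section 13.5 says risk-raising conditions are excluded, but known congenital long QT syndrome is not a listed exclusion, QT-prolonging medicines are not addressed, and no ECG is scheduled

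*Combined protocol and SAP*

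**What the plan says.** Section 13.5 gives three ways in which risk was kept down: a short intervention, proper conduct and monitoring, and selection of candidates. It describes the last as working "by excluding candidates with any condition that would increase the risk of adverse effects". The same section concedes that "it is unlikely that participation is associated with any sustained significant clinical benefit for the participants".

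Section 13.4.2 states: "Vorinostat should be administered with particular caution in patients with congenital long QT syndrome, and patients taking anti-arrhythmic medicines or other medicinal products". The sentence goes on to specify products that prolong the QT interval. Just before it comes this advice: "Baseline and periodic ECGs should be performed during treatment".

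The exclusions in 6.3 and the synopsis that come closest are:
- a general clause, "Known hypersensitivity to disulfiram or vorinostat or contraindications to treatment with these agents";
- laboratory limits that include "Serum potassium, magnesium, phosphorus outside normal limits" and low calcium;
- significant myocardial disease (myocarditis or reduced ejection fraction) and diagnosed coronary artery disease.

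Section 7.8 lists prohibited therapies, and starting any of them requires withdrawal from study drug. Under 7.7, other necessary treatment that, "in the opinion of the investigator, will not interfere with the study therapy, may be given at the discretion of the investigator". Section 6.5 allows withdrawal from study drug for "Any condition, interaction, or contraindication where continued participation in the study will result in an unacceptable risk for the participant".

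**The concern.** The risk/benefit section tells an ethics committee that candidates at raised risk of adverse effects are screened out. The protocol's own vorinostat section names a condition that calls for particular caution, yet the eligibility lists do not carry it. As the criteria stand, a candidate with known congenital long QT syndrome meets them unless the investigator decides otherwise, and two investigators could decide differently. Because the protocol expects no sustained benefit for participants, there is little to set against a risk that one line of text would avoid. What is at stake is the safety of a rare candidate and the accuracy of a sentence that supports the ethical justification. Efficacy inference is not at stake.

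**Working it through.** No figure in the plan needs reproducing. The check sets the sections against each other.

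**1. Is long QT a risk-raising condition in the protocol's own terms?** Yes. Section 13.4.2 singles it out for particular caution with one of the two study drugs.

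**2. Is it, or QT-prolonging medication, on any list?** Counting top-level items:

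| Place | Items | Naming long QT, arrhythmia or QT-prolonging medicines |
|---|---|---|
| 6.3 exclusions | 22 | 0 |
| Synopsis exclusions | 22 | 0 |
| 7.8 prohibited therapy | 7 | 0 |
| Visits with an ECG (Table 1, 8.2 to 8.10) | 9 | 0 |

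**3. Does another clause catch it?**
- The contraindications clause might. However, 13.4.2 uses the language of caution, so the clause does not clearly apply.
- The potassium, magnesium and calcium limits remove contributing factors, not the condition itself. The itemised screening chemistry in 8.2 lists potassium but neither magnesium nor calcium, although Table 1 refers to electrolytes generally.
- The cardiac exclusions cover muscle and coronary disease, not an electrical disorder.
- Section 7.7 asks whether a medicine would interfere with study therapy and does not mention QT.
- Sections 6.4 and 6.5 act through withdrawal after inclusion and are not entry criteria.

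**4. Would the schedule find it?** Medical history is taken at Visits 1 and 2, and medication is reviewed at all 9 visits. With no ECG scheduled, history is the only scheduled route, and it finds known cases only.

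**5. When should a co-medication decision be made?** Vorinostat starts on day 8, after seven days of disulfiram 2000 mg, and the primary endpoint is on day 11. Section 11.1 requires 14 participants and enrols 15, a margin of 15 − 14 = 1. If vorinostat were first withheld on day 8, that participant would reach the primary time point without the combination. Section 6.6 replaces people withdrawn before any study drug, but replaces those withdrawn later only case by case. Existing medicines are already recorded at screening, so the decision belongs at Visits 1 and 2.

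**6. Size.** Section 13.4.2 reports QTc prolongation in 3 of 86, 4 + 1 = 5 of 116, and 1 + 2 = 3 of 49 cancer-study patients, and no significant change in any of 24 after a single 800 mg dose. These figures do not measure risk in people with long QT syndrome, so I derive no event rate from them.

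**The case against.** The strongest reply is that no rule is broken. Section 13.4.2 asks for caution, and an investigator who weighs the risk and then enrols or declines has complied with it. The conflict is with one summary sentence in 13.5, read literally. That sentence would stay literally untrue after one exclusion is added, because 13.4.2 also asks for monitoring of thromboembolism and of diabetic patients, and neither is an exclusion. This stands, and it is why the fix also narrows 13.5.

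Exposure is also short: 3 + 3 = 6 vorinostat doses. The safeguards under step 3 are real, and together with medication review at every visit they give substantial partial protection. This stands too, and it keeps the point minor.

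It may seem uneven to exclude long QT while leaving co-medication to judgement. The difference is defensible. Section 13.5 speaks of conditions, and a known congenital condition can be settled at entry. Co-medication varies, and adding it to 7.8 would force withdrawal, which goes beyond the caution that 13.4.2 asks for.

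A reader might infer that long QT is a contraindication the protocol ignores, or that participants are not warned. The documents support neither. The wording is a caution, the consent pages were removed, and the disulfiram and vorinostat supply subsections under 7.3 are redacted and could contain precautions.

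**Conclusion.** The point holds as a minor mismatch between the risk/benefit statement and the enrolment criteria. Sections 13.4.2 and 13.5 together imply that known congenital long QT syndrome is kept out. The lists do not say so, QT-prolonging medicines are not addressed in 7.8, and the ECGs described in 13.4.2 are not in the schedule. The existing safeguards narrow the gap without clearly closing it.

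Perhaps none of 15 participants would be affected. A reader might infer a quantified cardiac risk for this trial, or a threat to the primary result. Neither follows: the documents give no event probability for these participants, and the primary comparison and its analysis are unaffected. The conclusion assumes that the redacted subsections do not add an eligibility rule, and that the contraindications clause is read in its ordinary sense.

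**What to change.** 1. Add *Known congenital long QT syndrome* to the exclusions in 6.3 and the synopsis, checked in the medical history already taken at Visits 1 and 2.
2. At the existing medication reviews at Visits 1 and 2, before the first disulfiram dose, identify any anti-arrhythmic or other QT-prolonging medicine and record the investigator's decision. Use the day 8 and day 22 reviews only for medicines newly started since then.
3. Reword 13.5 so that it refers to the conditions actually listed as exclusions.

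The cost is one criterion in two places, a short note at existing visits and one edited sentence, with no new visit, blood draw or test. The downside is that a rare candidate is not enrolled. Two limits remain: history finds only known cases, and which medicines count as QT-prolonging is still the investigator's judgement. These changes do not add the ECGs that 13.4.2 describes; scheduling them would be a separate decision for the sponsor.
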